7.3 Exclusion Criteria

Subjects who meet any of the following exclusion criteria will not qualify for entry into the study:

- 1. Anemia due to a cause other than CKD or subjects with active bleeding or recent blood loss
- 2. History of sickle cell disease, myelodysplastic syndromes, bone marrow fibrosis, hematologic malignancy, myeloma, hemolytic anemia, thalassemia, or pure red cell aplasia
- 3. Red blood cell (RBC) transfusion within 4 weeks prior to or during screening
- 4. Anticipated to recover adequate kidney function to no longer require dialysis
- Aspartate aminotransferase (AST)/serum glutamic oxaloacetic transaminase (SGOT), alanine aminotransferase (ALT)/serum glutamic pyruvic transaminase (SGPT), or total bilirubin >2.0 x upper limit of normal (ULN) during screening. Subjects with a history of Gilbert's syndrome are not excluded
- 6. Uncontrolled hypertension (defined as confirmed pre-dialysis systolic blood pressure >190 mmHg or diastolic blood pressure >110 mmHg at rest) during screening
- 7. Severe heart failure during screening (New York Heart Association Class IV)

- 8. Acute coronary syndrome (hospitalization for unstable angina or myocardial infarction), surgical or percutaneous intervention for coronary, cerebrovascular or peripheral artery disease (aortic or lower extremity), surgical or percutaneous valvular replacement or repair, sustained ventricular tachycardia, hospitalization for heart failure, or stroke within 12 weeks prior to or during screening
- 9. History of deep vein thrombosis (DVT) or pulmonary embolism (PE) within 8 weeks prior to or during screening
- 10. History of active malignancy within 2 years prior to or during screening, except for treated basal cell carcinoma of skin, curatively resected squamous cell carcinoma of skin, or cervical carcinoma in situ
- 11. History of hemosiderosis or hemochromatosis
- 12. History of prior organ transplantation or scheduled organ transplant (subjects on the kidney transplant wait-list or with a history of failed kidney transplant are not excluded), or prior hematopoietic stem cell or bone marrow transplant; note that corneal transplants and stem cell therapy for knee arthritis are not excluded
- 13. History of an acute or chronic infection requiring intravenous antibiotics within 4 weeks prior to randomization
- 14. Hypersensitivity to vadadustat, epoetin alfa, or any of their excipients
- 15. Use of an investigational medication or participation in an investigational study within 30 days or 5 half-lives of the investigational medication (whichever is longer), prior to screening
- 16. Previous participation in this study, previous participation in a Phase 3 study of vadadustat, or previous participation in a study with another hypoxia-inducible factor prolyl-hydroxylase inhibitor (HIF-PH inhibitor) other than vadadustat
- 17. Females subjects who are pregnant or breastfeeding; or female subjects of childbearing potential who are unable or unwilling to use an acceptable method of contraception (see Section 9.2.4)
- 18. Non-vasectomized male subjects who are unable or unwilling to use an acceptable method of contraception (see Section 9.2.4)
- 19. Any other reason, which in the opinion of the investigator, would make the subject not suitable for participation in the study

7.4 Retesting and Rescreening

7.4.1 Retesting

Retesting is defined as repeating laboratory tests within the same Screening Period.

All screening laboratory tests, including any repeat measurements, must be performed within the 28-day screening window with a minimum of 4 days between the last qualifying repeat measurement and the baseline visit on Day 1 (see Section 9.1).

Subjects who initially fail to qualify for the study based on laboratory test results may have their laboratory value retested once for each laboratory parameter within the 28-day screening period, at the investigator's discretion.

Retesting within the screening period does not constitute rescreening; however, if retesting falls outside of the screening period, it should be considered a rescreen (see Section 7.4.2).

For eligibility purposes, if Hb at screening visit 1 (SV1) is 10.0 to 10.5 g/dL, 1 retest complete blood count (CBC) should be performed prior to SV2. If the retest Hb is \geq 10.0 g/dL, the subject should not proceed with SV2. If the Hb at SV1 is >10.5 g/dL, the subject should not proceed with any further screening procedures at that time.

7.4.2 Rescreening

Subjects who fail to meet the qualifying criteria for Hb may be considered for rescreening outside of the initial 28-day screening period at the discretion of the investigator, if it is considered that the subject's status has changed and that the subject may now qualify for the study. Additionally, subjects who fail to qualify for the study based on low ferritin, TSAT, folate, or vitamin B12 values may be considered for rescreening after receiving appropriate replacement therapy.

Screening is limited to 3 attempts (the initial screening and 2 additional rescreening attempts). Subjects who fail to qualify for the study at the initial screening visit will receive a new subject number for each rescreening attempt. If rescreened, the subject will also sign a new informed consent form and will repeat all screening procedures for each rescreening attempt.

7.5 Study Completion, Study Termination, and Individual Study Site Termination

7.5.1 Study Completion

The study will be considered completed after all enrolled subjects have completed study participation, and the AE reporting period has been completed for each enrolled subject (see Section 10.3.1 for information regarding the AE reporting period).

7.5.2 Study Termination

The entire study may be suspended or terminated by the sponsor for safety or other unanticipated reasons or upon request of regulatory agencies. If this occurs, prompt notification will be given to investigators, Institutional Review Boards (IRBs), and regulatory authorities in accordance with regulatory requirements.

Criteria for premature study termination or suspension are detailed in Section 14.1.

7.5.3 Individual Study Site Termination

Study participation may be suspended or terminated at an individual investigational site for various reasons.

The investigator must notify the sponsor if the study is terminated by the investigator or the IRB at the site. If the investigator, IRB, or sponsor decides to terminate or suspend the study conduct at an investigative site for safety, non-enrollment, non-compliance with the protocol, or other unanticipated reasons, the above parties will be promptly notified.

Criteria and procedures for premature termination or suspension of an investigational site are detailed in Section 14.2 and Section 14.3.

7.6 Subject Completion and Individual Subject Discontinuation

NOTE: The need for rescue therapy does not constitute study completion and are not criteria for subject withdrawal from the study or permanent discontinuation of study drug (vadadustat or epoetin alfa).

7.6.1 Subject Completion

A subject will be considered as having completed the study after completing participation in the Week 24 visit (end of the 4-week safety follow-up period).

7.6.2 Individual Subject Study Drug Discontinuation or Individual Subject Discontinuation

The investigator must document the primary reason for temporary or permanent study drug discontinuation on the case report form (CRF). For subjects who discontinue study drug, the investigator should resume treatment based on standard of care and clinical judgment.

7.6.2.1 Interruption of Study Drug by Individual Subjects

Subjects who interrupt their study drug (vadadustat or epoetin alfa) after receiving the first dose on Day 1 and prior to completion of the study, should continue with the Schedule of Activities and safety assessments through Week 20, and should complete the 4-week safety follow-up period and the Week 24 visit assessments (see Appendix A).

During the study, it is anticipated that subjects may interrupt their study drug for any of the following reasons:

- Unacceptable toxicity or drug intolerability
- Investigator's discretion
- Adverse event
- Missed dialysis visit
- Other reasons

7.6.2.2 Permanent Discontinuation of Study Drug by Individual Subjects

NOTE: Subjects who permanently discontinue study drug (after randomization and prior to completion of the study drug treatment period) will complete the end-of-treatment (EOT) (Week 20) visit assessments within 1 day of stopping study drug (if possible), and should complete the 4-week safety follow-up period and the Week 24 visit assessments.

If a subject does not return for a scheduled visit, every effort should be made to contact the subject.

During the study, it is anticipated that subjects may permanently discontinue their study drug (vadadustat or epoetin alfa) for any of the following reasons:

- Unacceptable toxicity or drug intolerability
- Investigator's discretion
- Subject withdraws consent
- Subject becomes pregnant
- Receipt of kidney transplant
- Other reasons

8 STUDY DRUGS AND TREATMENT OF SUBJECTS

8.1 Epoetin Alfa

See the approved epoetin alfa US package insert for information on administration and storage.

Epoetin alfa solution for intravenous injection in single-dose or multi-dose vials (ie, 2000, 3000, 4000, 10000, and 20000 units/mL) will be provided by the sites in commercially-approved primary packaging and stored per the approved label.

Epoetin alfa will be administered to subjects by site staff in accordance with the approved label. The prescribed and actual dose of epoetin alfa administered will be documented in the subject's medical records.

8.2 Vadadustat

8.2.1 Study Drugs, Supplies, and Storage

The starting dose of vadadustat is

once daily) and allowed doses include

Vadadustat is formulated for oral dosing. The tablets are white to off-white, round, bi-convex film-coated tablets (8 mm diameter) containing 150 mg vadadustat and the following inactive ingredients: microcrystalline cellulose (MCC), sodium starch glycolate, hydroxypropyl methylcellulose (HPMC), colloidal silicon dioxide, and magnesium stearate, and a film coating.

Vadadustat tablets will be provided to sites by the sponsor or its designee.

Vadadustat should be stored per the product label. A min-max thermometer is preferred for this study. A temperature log should be maintained with drug storage temperatures recorded in accordance with the pharmacy manual.

All study drug supplies must be kept in a locked facility and accessible only to authorized study personnel.

Packaging and labeling will be in accordance with current Good Manufacturing Practice and local regulatory requirements.

8.2.2 Dispensing Procedures for Vadadustat

The site pharmacist or designated study personnel will be responsible for preparing study drugs for dispensation, and will maintain an investigational medication distribution form itemizing all study drugs dispensed to and returned from each subject during the study.

At the baseline (Day 1) visit, subjects who are randomized to the vadadustat treatment arm will be provided with 1 bottle of vadadustat. Each bottle of vadadustat will contain 100 tablets of vadadustat (150 mg/tablet).

Subjects should be instructed to bring unused vadadustat and empty bottles to each study visit for product accountability. Subjects will be instructed to finish 1 bottle before opening a new bottle.

Empty bottles will be collected at the study visits. Previously dispensed bottles (whether opened or unopened) with remaining tablets may be re-dispensed to the subject during the dosing phase of the study.

Resupply of additional vadadustat at subsequent visits will be managed via the IWR system and will be dependent on the current dose level of vadadustat and the number of tablets remaining in the subject's current vadadustat supply at a given study visit.

8.2.3 Product Accountability and Destruction

Vadadustat accountability should be an ongoing process throughout the study. Vadadustat must be accounted for and any discrepancies explained. The designated study personnel are responsible for keeping accurate records of the clinical supplies, all supplies retained in inventory at the investigative site, and study drug dispensed to or returned from each subject. Records should be maintained that accurately reflect the drug accountability throughout the study.

Proper drug accountability includes, but is not limited to:

- Continuously monitoring expiration dates, if expiry date or retest date is provided to the site
- Frequently verifying that actual inventory matches documented inventory
- Verifying that the log is completed for all drug received and that all required fields are complete, accurate, and legible.

If any dispensing errors or discrepancies are discovered, the sponsor or designee must be notified immediately.

During the study, the investigator will be notified of any expiry dates or retest date extensions of clinical study material. If an expiry date notification is received during the study, the investigative site must complete all instructions outlined in the notification, including segregation of expired clinical study material for return to the sponsor or its designee for destruction.

Prior to investigative site closure and at appropriate intervals during the study, a representative from the sponsor will perform clinical study material accountability and reconciliation.

At the end of the study, the investigator will retain all original documentation regarding clinical study material accountability, return, or destruction, and copies will be sent to the sponsor or designee.

All unused or partially used study drug should be returned to the sponsor or destroyed at the investigational site, as specified by the sponsor. Appropriate records of the disposal will be documented and maintained. No unused study drug may be disposed of until fully accounted for by the sponsor's monitor or designee. Empty containers may be disposed of in accordance with local procedures.

8.3 Treatment of Subjects

Study drug treatment will aim to maintain Hb level within target range of 10.0 to 11.0 g/dL.

8.3.1 Randomized Treatment Group Assignments

Subjects will be randomly allocated (1:1 ratio) via the IWR system to participate in either the vadadustat treatment arm or the epoetin alfa treatment arm. On Day 1, subjects will withhold dosing until it is confirmed which treatment arm (vadadustat or epoetin alfa) they are assigned to.

8.3.2 Blinding During the Study

This is an open-label study and will not involve any blinding procedures.

8.3.3 Measurement of Hemoglobin Levels for Dose Adjustment Consideration

Hemoglobin values will be measured by a central laboratory. Study drug treatment will aim to maintain Hb level within target range of 10.0 to 11.0 g/dL. Hemoglobin will be monitored throughout the study to determine the dose of study medication (vadadustat or epoetin alfa) that subjects should receive. Refer to Section 8.3.5. Hb levels can be measured more frequently based on investigator's clinical judgment.

If dose adjustment is recommended based on Hb value and protocol-specified guidelines, dosing instructions can be provided to the subject during the next dialysis session at the investigative site (or dialysis center) or during an unscheduled site visit within 3 business days after receiving the Hb result from the central laboratory. If scheduling the subject within this time frame is not possible, dosing instructions will be provided to the subject over the telephone.

8.3.4 Dosing Regimen for the Epoetin Alfa Treatment Arm

For subjects who are randomized to the epoetin alfa treatment arm, the initial dosing regimen in the study (starting from baseline [Day 1] visit) will be the same dose that they were receiving during the screening period.

Epoetin alfa dose will be administered and titrated as clinically indicated based on an individual subject's central lab Hb value and the approved label for adult patients with CKD on dialysis.

8.3.5 Dosing Regimen for the Vadadustat Treatment Arm and Guidelines for Vadadustat Dose Adjustment

Subjects assigned to the vadadustat arm will discontinue epoetin alfa and take vadadustat once daily for 20 weeks.

The following dosing regimen are for subjects who are randomized to the vadadustat treatment arm:

- Vadadustat dosing (Day 1 to Week 20)
 - Starting dose of vadadustat: once daily) starting at baseline/Day 1. The first dose of vadadustat will be administered at the investigative site after other baseline procedures have been completed. Thereafter, vadadustat will be taken once daily in the dialysis centers or on an outpatient basis.
 - The vadadustat dose can be up-titrated every 4 weeks or down-titrated more frequently based on the target Hb range of 10.0-11.0 g/dL.

 - Dosing instructions: Subjects should be instructed to swallow intact tablet(s) of vadadustat with water or another beverage. Subjects may take vadadustat with or without food. The full dose should be taken at approximately the same time each day. The subject should be instructed to take any oral iron supplements (including multivitamins containing iron), iron containing phosphate binders, or any medication containing iron at least 2 hours before or 2 hours after taking the vadadustat dose.
 - After the end of vadadustat treatment at Week 20 (or following early discontinuation of vadadustat), subjects will resume dosing with epoetin alfa (or another ESA), based on the approved label for adult patients with CKD on dialysis.

Guidelines for Vadadustat Dose Adjustments

Vadadustat dose adjustments will be guided by an IWR system based on the Hb value and programmed Dose Adjustment Algorithms (as presented below).

When adjusting vadadustat dose, investigators should consider Hb rate of rise, rate of decline, and the subject's clinical condition (eg, recent illness, volume depletion, and volume overload). In cases of extenuating clinical circumstances, the investigator may elect to dose outside the IWR system dosing recommendation to maintain the Hb within the target range. In such cases, the clinical circumstances must be documented in the subject's record and IWR system.

- Do not increase the vadadustat dose more frequently than once every 4 weeks. Decreases in vadadustat dose can occur more frequently. Avoid frequent vadadustat dose adjustments.
- If a dose adjustment is required to maintain Hb within the target range (10.0-11.0 g/dL), then increase or decrease the vadadustat dose by 1 tablet.
- If the Hb decreases below 10.0 g/dL, increase the dose of vadadustat by 1 tablet.
- If the Hb exceeds 11.0 g/dL, interrupt vadadustat until Hb decreases to 11.0 g/dL or less, then resume dosing of vadadustat with 1 fewer tablet.

NOTE: If subject was on 1 tablet prior to interruption, then resume dosing with 1 tablet.

• If the Hb increases rapidly (eg, >1.0 g/dL in any 2-week period or >2.0 g/dL in any 4-week period), and a subject is not receiving epoetin alfa, decrease the dose of vadadustat by 1 tablet.

8.3.6 Late or Missed Doses of Study Drug Treatment

Subjects on vadadustat should be instructed to take the study drug at approximately the same time each day. If a dose is forgotten, subjects should be instructed to take the dose as soon as they remember during the same day. If a forgotten dose is not remembered on the same day, the subject should skip the dose and resume the normal dosing schedule the following day. Subjects should not double-up on missed doses.

Epoetin alfa dose (including handling of late or missed dose) should be administered as clinically indicated based on an individual subject's Hb value and the approved label for adult patients with CKD on dialysis.

8.3.7 Compliance with Vadadustat Treatment

Subjects will be questioned regarding dosing compliance and whether they have questions or have experienced any problems related to vadadustat dosing. The investigator will also maintain drug accountability logs itemizing vadadustat dispensed to and returned from each subject during the study. Treatment compliance will be determined from these forms along with the subject questioning.

Subjects who miss doses will be counseled on the importance of compliance.

NOTE: At the Week 2 and Week 18 visits, subjects in the vadadustat treatment arm should be reminded and instructed to hold their vadadustat dose on the day of the Week 4 and Week 20 visits (respectively). This is because a blood sample for PK analysis will be collected on the day of the Week 4 and Week 20 visits before the vadadustat dose is administered at the investigative site.

Subjects will also be questioned regarding the timing of their last dose of vadadustat during PK sample collection at the Day 1 visit and Week 4 and Week 20 visits. The date and time of these doses should be recorded.

8.3.8 Continuation of Study Drug Treatment

Subjects in the vadadustat treatment arm will not receive vadadustat past the treatment period of approximately 20 weeks. Subjects in the vadadustat treatment arm who complete Week 20, or discontinue early, will resume dosing with epoetin alfa (or another ESA) at Week 20 after all EOT procedures are completed.

8.3.9 Iron Supplementation (Information on Allowed Use)

Investigators should prescribe iron supplementation (intravenous, oral, or intradialytic) as needed and maintain ferritin \geq 100 ng/mL and TSAT \geq 20%. The duration, dosage, and frequency of use of supplemental iron should be recorded.

Important: Because of the potential for oral iron to decrease the bioavailability of vadadustat, vadadustat should not be administered concurrently with an oral iron supplements (including

multivitamins containing iron), iron containing phosphate binders, or any medications containing iron. Subjects should be instructed to take any of these medications at least 2 hours before or 2 hours after taking the dose of vadadustat.

8.3.10 Rescue Therapy Guidelines

Hemoglobin levels will be monitored throughout the study at scheduled visits and can be measured more frequently based on investigator's clinical judgment.

Rescue therapy with RBC transfusion or epoetin alfa are allowed, but not required during the treatment period. The following rescue therapy guidelines are provided to ensure the safety of study subjects and to standardize the use of rescue in the study. In cases of extenuating clinical circumstances, the investigator may elect to dose outside the rescue therapy guidelines to maintain the Hb within the target range. In such cases, the clinical circumstances should be documented in the subject's record.

- RBC transfusion: Investigators should use their investigative site's transfusion guidelines when determining whether to transfuse a study subject. In general, in the event of an acute or severe loss of blood, RBC transfusion should be administered as clinically indicated. In less severe instances but where there may be worsening of anemia or moderate to severe symptoms of anemia, RBC transfusions are permitted based on the investigator's clinical judgment. Study drug (vadadustat or epoetin alfa) may be continued during the RBC transfusion period.
 - Epoetin alfa rescue therapy: Starting at Week 6, subjects in both treatment arms will be allowed (although not required) to have their Hb rescued with epoetin alfa. When possible, a subject on vadadustat should be on maximum dose of vadadustat for 2 weeks prior to epoetin alfa rescue. Epoetin alfa rescue therapy should be administered based on the approved US product label for adult patients with CKD on dialysis.
 - To qualify for epoetin alfa rescue therapy, each of the following conditions must be fulfilled.

NOTE: Epoetin alfa rescue therapy should be stopped when Hb is ≥ 9.0 g/dL.

- The subject has experienced a clinically significant worsening of their anemia or symptoms of anemia (eg, fatigue, weakness, shortness of breath, chest pain, confusion, or dizziness) compared to baseline
- The subject's Hb is confirmed to be <9.0 g/dL
- The Hb level decreased >0.5 g/dL from baseline
- Reducing the risk of alloimmunization or transfusion-related risks or both is a goal
- For the epoetin alfa treatment arm:
 - In addition to meeting the rescue criteria noted above, dosing and administration of epoetin alfa rescue therapy should be based on the approved label for adult patients with CKD on dialysis.

- For the vadadustat treatment arm:
 - Epoetin alfa rescue may not be considered until the next study visit if a subject's current vadadustat dose can be increased (ie, if the subject's last vadadustat dose increase was at least 4 weeks earlier and the subject is currently receiving a vadadustat dose of 600 mg/day or less, then vadadustat dose can be increased by 1 tablet to maintain Hb within the target range of 10.0-11.0 g/dL).

NOTE: vadadustat must be temporarily interrupted during epoetin alfa rescue therapy. After epoetin alfa rescue therapy is completed, vadadustat should be resumed and adjusted per the dose adjustment guidelines (Section 8.3.5).

A minimum interval must be observed prior to restarting vadadustat after the last dose of rescue medication, and treatment may be resumed 2 days after last dose of epoetin alfa rescue.

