8.4.2 Erythropoiesis-Stimulating Agents

Subjects are prohibited from taking non-protocol ESAs starting from the screening period and through Week 20, unless the subject permanently discontinues study treatment.

Epoetin alfa rescue therapy is allowed as presented in Section 8.3.10.

8.4.3 RBC Transfusion, Epoetin Alfa Rescue Therapy, Iron Supplementation, and Therapeutic Phlebotomy

Use of epoetin alfa rescue therapy, iron supplementation, and therapeutic phlebotomy within 30 days prior to Day 1 will be recorded.

Receipt of RBC transfusion, epoetin alfa rescue therapy, iron supplementation, and therapeutic phlebotomy during the study will be recorded.

NOTE: RBC transfusion within 4 weeks prior to or during screening is a study exclusion criterion.

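### In the epoetin arm, a dose increase that meets the rescue conditions can be recorded as titration or as rescue; separately, the per-protocol epoetin-dose clause does not fit the vadadustat arm

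*Combined protocol and SAP*

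**What the plan says.** **Titration, epoetin arm (Section 8.3.4).** "Epoetin alfa dose will be administered and titrated as clinically indicated based on an individual subject's central lab Hb value and the approved label". Section 8.3 sets the aim for both arms at Hb 10.0 to 11.0 g/dL.

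**Rescue, both arms (Section 8.3.10 and its synopsis copy).** From Week 6, "subjects in both treatment arms will be allowed (although not required) to have their Hb rescued with epoetin alfa". Four conditions must all hold: clinically significant worsening of anemia or its symptoms, confirmed Hb below 9.0 g/dL, a fall of more than 0.5 g/dL from baseline, and a goal of reducing alloimmunization or transfusion risk. For the stop rule, "Epoetin alfa rescue therapy should be stopped when Hb is" at or above 9.0 g/dL. For the epoetin arm the section adds only: "In addition to meeting the rescue criteria noted above, dosing and administration of epoetin alfa rescue therapy should be based on the approved label". In documented extenuating circumstances, "the investigator may elect to dose outside the rescue therapy guidelines to maintain the Hb within the target range".

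**Vadadustat arm.** Section 8.3.10 says "vadadustat must be temporarily interrupted during epoetin alfa rescue therapy". Section 8.4.2 says "Subjects are prohibited from taking non-protocol ESAs starting from the screening period and through Week 20, unless the subject permanently discontinues study treatment".

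**Recording.** Section 8.4.3: "Receipt of RBC transfusion, epoetin alfa rescue therapy, iron supplementation, and therapeutic phlebotomy during the study will be recorded". Section 8.1 has prescribed and actual epoetin doses documented in the medical record.

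**Use.** The proportion receiving epoetin rescue is a secondary endpoint (Section 5.2), summarized by treatment group (Section 11.6). Section 11.2 admits a subject to the per-protocol set only with an epoetin dose recorded in Weeks 18 to 20 and no rescue in Weeks 12 to 20.

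**The concern.** In the control arm the rescue drug is the study drug, and both routes take the dose from the same label. If a control subject meets the four conditions and the site raises the dose, one site may enter rescue and another titration, and both would be following the protocol. Treatment is open-label, so the person choosing the label knows the arm.

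Three things are at stake. The two arms' rescue proportions would not be counted on the same basis. The rescue part of per-protocol membership would turn on the same label. And the stop at 9.0 g/dL conflicts with continuing study epoetin toward 10.0 to 11.0 g/dL, because a site that labels an increase as rescue is told to stop 1.0 to 2.0 g/dL below the arm's target.

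The per-protocol dose clause is a separate fault. It asks vadadustat subjects for a drug that the protocol has them discontinue on Day 1.

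**Working it through.** **1. The plan's own figure.** Section 11.1 plans about 50 subjects, 25 per arm, and gives no alpha, power, effect size or SD. There is no calculation to reproduce. No rescue rate is given either.

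**2. The two routes in the epoetin arm.**

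| | Titration (8.3.4) | Rescue (8.3.10) |
|---|---|---|
| Drug | epoetin alfa | epoetin alfa |
| Dosing source | approved label | approved label |
| When | Day 1 to Week 20 | from Week 6, four conditions |
| Required? | as clinically indicated | allowed, not required |
| End point | aim 10.0 to 11.0 g/dL | stop at 9.0 g/dL or above |

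Titration is not suspended when the conditions hold, and rescue is optional, so meeting the conditions does not make an increase a rescue. No increment, separate order or add-on rule marks it as one. The two routes differ only in how they end, and that does not tell a site what to enter at the start. Sections 8.1, 8.4.3 and 9.4 require doses and rescue use to be recorded or reviewed, but do not classify an increase that fits both. Section 11 gives no definition of rescue for analysis.

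**3. Extent of the overlap.** The Hb conditions amount to Hb below min(9.0, baseline − 0.5):
- baseline 8.5: below 8.0 g/dL
- baseline 9.0: below 8.5 g/dL
- baseline 9.5 or more: below 9.0 g/dL

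Before Week 6, or when any condition fails, an increase is titration, apart from documented extenuating-circumstances dosing.

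**4. Effect of the label.** Assume that k of 25 control subjects meet all conditions and receive more epoetin. The recorded proportion then runs from 0/25 (none labelled rescue) to k/25 (all labelled). Intervals are exact (Clopper-Pearson) 95%.

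| k | None labelled | All labelled | Largest per-protocol n if in Weeks 12–20 |
|---|---|---|---|
| 2 | 0% (0–13.7%) | 8% (1.0–26.0%) | 25 − 2 = 23 |
| 3 | 0% (0–13.7%) | 12% (2.5–31.2%) | 25 − 3 = 22 |
| 5 | 0% (0–13.7%) | 20% (6.8–40.7%) | 25 − 5 = 20 |

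With vadadustat-arm rescue assumed at 5/25 = 20%, the difference between arms (vadadustat minus epoetin) is +20 points if none are labelled. If all are labelled, it is +12, +8 or 0 points for k = 2, 3 or 5.

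**5. Could subjects reach the overlap?** This is an illustration with every input assumed: true mean Hb uniform on 8.6 to 9.9, visit SD 0.4 to 0.6, autocorrelation 0 or 0.5, both screening values within 8.5 to 10, and baseline the mean of the screening and Day 1 values. The share meeting the two Hb conditions at two consecutive scheduled visits in Weeks 6 to 20 is:
- mean Hb unchanged: about 11–35%
- rising 0.6 g/dL by Week 20: about 1–14%
- 0.3 g/dL lower throughout: about 40–57%

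These are not bounds. The two clinical conditions lower the figures, and extra Hb measurements raise them.

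**6. The per-protocol dose clause in the vadadustat arm.**
- On vadadustat, no epoetin in Weeks 18 to 20: fails the dose clause.
- On vadadustat, epoetin rescue in Weeks 18 to 20: fails the no-rescue clause.
- On vadadustat to Week 20, first epoetin at the Week 20 resumption (Section 8.3.8): passes only if that dose counts as inside the window.
- Stopped vadadustat early and resumed epoetin: has a dose in the window that is not rescue, so can pass.

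Read literally, the clause removes on-treatment subjects and can keep those who left treatment.

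**The case against.** Several counterarguments stand in part.

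- *The two acts are not identical.* Correct. Rescue ends at 9.0 g/dL and titration continues, so the overlap is exact only for starting an increase.
- *The vadadustat arm is not free of ambiguity.* Correct. Section 8.4.2 bars non-protocol ESAs, and epoetin is a protocol drug. Section 7.6.2 covers temporary as well as permanent discontinuation and refers to standard of care. Epoetin given during a temporary interruption therefore has no clear label. This is much narrower than in the control arm, where every qualifying increase is affected.
- *Doses and two-weekly Hb are recorded, so analysts could impose a rule later.* Partly. A uniform Hb-and-dose rule could be applied, but which label the site intended could not be recovered, and a rule set after the data are seen is weaker than one set now. CRF completion instructions may hold such a rule; they are not among the documents.
- *The size is guesswork.* Correct. The simulated shares depend wholly on assumed inputs and are too wide to serve as an estimate.
- *The simplest cure is to abolish rescue in the control arm.* This would contradict the provision for both arms, make the control proportion zero by construction, and make per-protocol exclusion differ by arm. The fix below keeps rescue in both arms.

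A reader might infer that the primary result is compromised. The documents do not support that: Section 11.5 bases the primary analysis on observed data without imputation, MITT membership does not depend on rescue, and no formal test is planned. Nor do they support reading the control arm as lacking a dosing rule or having a different target. Label-based titration is an acceptable rule, and both arms share one Hb range.

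**Conclusion.** The point holds within limits. From Week 6, once all four conditions are met, the plan does not say whether starting an epoetin increase in the epoetin arm is titration or rescue. The control-arm rescue proportion and the rescue part of per-protocol membership therefore rest on site labelling, while the vadadustat-arm count largely does not. The 9.0 g/dL stop needs reconciling with titration in the epoetin arm. The Week 18 to 20 epoetin-dose clause is wrong as written for the vadadustat arm, and this does not depend on any assumption about rates.

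The size of the labelling effect cannot be fixed from the documents. What is certain is the step of 4 points (1/25) per relabelled control subject, taking the planned 25 as denominator. The effect is confined to one secondary endpoint and the per-protocol set of an exploratory study, so this is a change worth considering rather than an obstacle to the trial.

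**What to change.** **(a) Section 8.3.10 and its synopsis copy.** Keep rescue in both arms and add: *In the epoetin alfa arm, an epoetin dose increase ordered from Week 6 when all four conditions are documented is recorded as epoetin alfa rescue; all other increases are titration under Section 8.3.4. The stop at 9.0 g/dL ends the rescue episode and does not limit titration under Section 8.3.4.*

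**(b) Section 11.6.** Beside recorded rescue and RBC transfusion, show for both arms the proportion with two consecutive scheduled central-lab Hb values below 9.0 g/dL and more than 0.5 g/dL below baseline in Weeks 6 to 20. Note that treatment after the first low value can affect it.

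**(c) Section 11.2.** Limit the Week 18 to 20 epoetin-dose clause to the epoetin arm. Apply one rescue definition to both arms for the Week 12 to 20 exclusion: RBC transfusion, or epoetin rescue under Section 8.3.10 as amended in (a), not counting the Week 20 resumption. Use MITT for reading results by arm. This stops the loss of on-treatment vadadustat subjects but does not remove those who stopped early. If the set is meant to be on treatment at the end, the matching clause would be a vadadustat dose in the same window.

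**Cost.** Wording in three sections and the synopsis, plus one table row from Hb already collected every 2 weeks. No extra visits, tests or patients. There is slightly more analysis work, and the control-arm rescue count still depends on sites documenting the two clinical conditions.
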